4.2.4.2 Sensitivity analyses

Controlled imputation

To examine the sensitivity of the results of the primary analysis to departures from the underlying assumptions about missing data, controlled multiple imputation analyses will be performed which allow for different underlying assumptions to be used.

An underlying negative binomial stochastic process for the number of exacerbations will be assumed and post-study withdrawal counts will be imputed conditional upon the observed number of events prior to the withdrawal under both MAR and missing not at random (MNAR)/dropout reason-based (DRMI) assumptions respectively:

- a) MAR: Missing counts in each arm will be imputed assuming the estimated event rate within that treatment group.
- b) MNAR/DRMI: Missing counts will be imputed differently depending on the reason for dropout.

Missing counts for subjects in the tezepelumab arm who dropped out for a treatment-related reason will be imputed based on the estimated event rate in the placebo arm (the "copy reference" approach), whereas the remaining subjects who dropped out will be imputed assuming MAR.

Table 7 summarises how tezepelumab subjects withdrawing from study will be handled in the DRMI analyses described above. The rules in the table will be applied irrespective of the length of time between discontinuing IP and withdrawing from study (noting that the treatment policy strategy is used for these sensitivity analyses).

Table 7 Treatment arms for imputation of tezepelumab subjects under DRMI

Reason for withdrawing from study	Reason for discontinuing IP	DRMI
Death		Placebo
Site terminated by sponsor		Tezepelumab
Study terminated by sponsor		Tezepelumab
Loss to follow-up Withdrawal by Subject Withdrawal by parent/guardian Other	Death	Placebo
	Adverse event	Placebo
	Development of study-specific discontinuation criteria	Placebo
	Severe non-compliance to protocol	Placebo
	Subject lost to follow-up	Placebo by default (pending blinded review of any further information)
	Subject decision	Placebo by default (pending blinded review of any further information)
	Other	Placebo by default (pending blinded review of any further information)

A blinded review of subjects who discontinued IP for reasons of “Subject lost to follow-up”, “Subject decision” or “Other” will be performed prior to unblinding at the primary database lock. A listing of these subjects and the assumptions made under DRMI will be documented. If any recorded comments (on either of the “Discontinuation of Investigational Product” or “Disposition” eCRF pages) indicate clearly that the reason for study withdrawal was not related to treatment, then the “Placebo” default for DRMI in the above table may be changed for that subject.

The methodology used for sensitivity analysis is described in more detail in [Keene et al., 2014](#). The steps for carrying out multiple imputation are outlined below.

Step 1: Fitting a negative binomial model to the observed data

A negative binomial regression model will be fitted to the observed exacerbation data with treatment group, region, age and history of exacerbations included as covariates. The logarithm of the time at risk (in years) for exacerbation will be used as an offset variable in the model.

Step 2: Drawing samples from the posterior distribution

The negative binomial distribution is conventionally defined as the probability distribution of the number of successes Y before k failures are seen in a series of independent Bernoulli trials with probability p of success and $(1-p)$ of failure.

The posterior distribution for parameter k and coefficients β will be created as a product of non-informative prior and the likelihood from the model in Step 1. A uniform prior distribution will be assumed for the regression coefficients. A Gamma (10^{-4} , 10^{-4}) will be assumed for $1/k$.

With the use of Markov Chain Monte Carlo (MCMC) method, 100 samples of k and β will be drawn from their posterior distribution. Convergence of the MCMC algorithm will be assessed.

A random seed of 991511 will be used. The first 2000 iterations will be discarded to allow for convergence to a stationary distribution and to remove the effect of the starting values (“burn-in”). A gap of 100 iterations will be used between imputations to ensure independence between imputations (“thinning”).

Step 3: Imputing missing data

For a subject who withdrew from the study early, let Y_1 denote the number of events prior to withdrawal (over time t_1), and let Y_2 denote the number of unobserved events after withdrawal until the end of the study's planned treatment period (over time t_2). For a subject who completes the planned treatment period, Y_1 denotes the number of events prior to completion (over time t_1). Using the formula in [Keene et al., 2014](#), the unobserved events Y_2 will be imputed from a negative binomial distribution with parameters k^* and p^* , where:

- $k^* = k + Y_1$
- $p^* = (k + \varphi_1) / (k + \varphi_1 + \varphi_2)$
- φ_1 is the expected number of events prior to withdrawal
- φ_2 is the expected number of events after withdrawal

Thus, $Y_1 + Y_2$ gives the number of exacerbations (observed and imputed) over the planned treatment period, $t_1 + t_2$. A random seed of 112358 will be used for the imputation.

The parameters φ_1 and φ_2 will be derived for each set of β and k parameters sampled in Step 2 under 2 different missing data scenarios, MAR and DRMI.

Step 4: Multiple imputation algorithm

For each scenario detailed in Step 3, the algorithm for implementing multiple imputation is:

- i. Select the first set of parameters $(\hat{\beta}, \hat{k})$ from Step 2
- ii. Impute Y_2 for each subject who discontinued from the study early, using the method outlined in Step 3
- iii. Calculate $Y_3 = Y_1 + Y_2$ for all subjects, where $Y_2 = 0$ for subjects who completed the study and $Y_2 \geq 0$ for subjects who discontinued from the study early.
- iv. A negative binomial regression model will be fitted using Y_3 as the response variable with treatment group, region, age and history of exacerbations included as covariates. For subjects completing the planned treatment period, the offset will be the logarithm of the time at risk (in years) for exacerbation. For subjects with an imputed number of exacerbations after withdrawal, the offset will be the logarithm of the study's planned treatment period excluding the time during an observed exacerbation and the 7 days following an observed exacerbation.
- v. Using the model from (iv) calculate treatment differences for the comparisons of interest
- vi. Select the next set of parameters $(\hat{\beta}, \hat{k})$ from Step 2 and repeat (ii) through to (v) a further 99 times.
- vii. Using Rubin's formulae, summarise the sets of treatment differences in (v) to give an overall treatment difference for the comparisons of interest with 95% confidence limits. The number of events and total time at-risk will be derived by taking the arithmetic mean of these values across the sets of data.
- viii. Back-transform the estimates and 95% confidence limits to give a rate ratio and corresponding limits

Tipping point analysis

A tipping point analysis will be performed for the primary endpoint, using similar multiple imputation methodology to examine the impact of varying the rate parameter for missing data in subjects who withdrew from the study early.

In this analysis, various degrees of improvement in the placebo group p_p after withdrawal, and various degrees of worsening in the tezepelumab group δ_T after withdrawal, will be simultaneously explored.

Missing data will be imputed for Placebo subjects who withdrew from the study (irrespective of reason for discontinuing IP or study), by multiplying the estimated Placebo exacerbation rate-by an improvement factor δ_P .

Missing data will be imputed for tezepelumab subjects who withdrew from the study (irrespective of reason for discontinuing IP or study), by multiplying the estimated Tezepelumab exacerbation rate by a worsening factor δ_T .

Tipping points are defined as the range of smallest values (δ_P, δ_T) which would result in a change of conclusion, the latter being assessed according to the nominal statistical significance levels applied in [Section 4.1.2](#).

Imputation will be performed within each treatment arm, and therefore $(\delta_P, \delta_T) = (1, 1)$ corresponds to the MAR analysis:

- $\log(\delta_P)$ will be varied from -1.5 to 0 in increments of 0.5
- $\log(\delta_T)$ will be varied from 0 to 1.5 in increments of 0.5.

This corresponds to values of δ_P between 0.22 and 1, and values of δ_T between 1 and 4.5. If a tipping point was observed with analysis using 0.5 increments, smaller increments e.g. of 0.25 may need to be explored in the relevant range to determine the tipping point more precisely.

4.2.4.3 Supplementary analyses

The primary analysis specified in [Section 4.2.4.1](#) will be repeated using on-treatment data only, where the definition of on-treatment is given in [Section 2.1.5](#).

4.2.4.4 Supporting analyses

Annualised rates for those exacerbations due to ER visits or hospitalisations (a subset of the primary endpoint defined in [Section 3.2.1.1](#), specifically the 2nd and 3rd bullets only) will be summarised descriptively and analysed using a similar model as for the primary analysis.

Annualised exacerbation rates which consider adjudicated outcomes (see [Section 3.2.3.1](#) for details) will also be analysed similarly to the primary analysis. The analysis which considers adjudicated outcomes will also be performed for the exacerbations due to ER visits or hospitalisations and exacerbations due to hospitalisations.

Annualised rate for those exacerbations due to hospitalisations only (a subset of the primary endpoint defined in [Section 3.2.1.1](#), specifically the 3rd bullet only) will be summarised descriptively and analysed using a similar model as for the primary analysis.

These supporting analyses will be performed using the treatment policy strategy only.

Analysis of the time to first exacerbation is described in [Section 4.2.6](#), since this is defined as a secondary endpoint.

4.2.4.5 Assessing efficacy across phenotypes and other baseline characteristics

Efficacy for the primary endpoint will be evaluated separately for biomarkers of interest (which comprises an evaluation of both categorical subgroups and the continuous biomarker

variable), and other exploratory variables (which comprises an evaluation of categorical subgroups only).

Descriptive summaries of the AAER will be presented for the specified categorical variables below, irrespective of how few subjects there are in any particular subgroups.

For model-based analyses, if any of the subgroups have fewer than 10 subjects in one or both treatment groups, this subgroup level will not be included in the model. If that leaves only one subgroup level, the model will not be fitted for that categorical variable. If it leaves more than one subgroup level, the model will be fitted using the remaining subgroups which have 10 or more subjects in both treatment groups.

Biomarkers of interest

Descriptive summaries of the AAER by treatment group will be produced for each of the following categorical variables:

- Baseline eosinophils group: $<300/\mu\text{L}$, $\geq 300/\mu\text{L}$
- Baseline eosinophils group: $<150/\mu\text{L}$, $150-<300/\mu\text{L}$, $300-<450/\mu\text{L}$, $\geq 450/\mu\text{L}$
- Baseline eosinophils group: $<150/\mu\text{L}$, $\geq 150/\mu\text{L}$
- Baseline clinic visit FENO group: $<25\text{ppb}$, $\geq 25\text{ppb}$
- Baseline clinic visit FENO group: $<25\text{ppb}$, $25-<50\text{ppb}$, $\geq 50\text{ppb}$
- Baseline perennial specific IgE status (FEIA): Any perennial FEIA positive, All perennial FEIA negative, Unknown perennial FEIA

A similar negative binomial model will be fitted as for the primary analysis for each of the above variables in turn, with additional factors for the subgroup variable and the treatment by subgroup interaction. This model will be used to estimate the treatment effect and its 95% CI within each of the subgroup categories, which will be tabulated and also summarised graphically using a forest plot. The overall treatment effect will be displayed on the forest plot. This includes the analysis of AAER in subjects with baseline eosinophils $< 300/\mu\text{L}$ which is specified in [Section 4.1.2](#).

A p-value for the treatment by subgroup interaction will not be presented for each of these models due to the various difficulties in interpretation, which arise from both low power and an inflated chance of false positive findings.

The probability of a chance finding will be assessed using a standardised effect plot. This plot will present the estimated effects for each subgroup category (estimated from the above models and ordered from largest to smallest), for all subgroup variables together as listed above, along with reference lines for what would be expected for the most extreme

observations by chance (when there was no treatment by subgroup interaction), as taken from a permutation distribution. Observed values falling outside of these reference lines will be investigated further in terms of the plausibility and causes of such an effect. Further graphical analysis may be performed to aid interpretation if necessary.

Any unexpected observed pattern may also be further explored using resampling techniques, where null hypothesis data will be generated (in many iterations) to assess the probability of seeing a pattern as strong (or stronger) by chance only; the null hypothesis will correspond to keeping the main effects intact whilst breaking any potential predictive property of the biomarkers.

A locally estimated scatterplot smoothing (LOESS) plot will be produced for each of the continuous biomarker variables (baseline eosinophils (cells/ μ L), baseline FENO (ppb) and baseline total serum IgE (IU/mL)).

The categorical subgroup analysis above will also be repeated using the four (mutually exclusive) categories defined by the quartiles of each baseline biomarker.

Other exploratory variables

Descriptive summaries of the AAER by treatment group will be produced for each of the following categorical variables:

- ICS dose at study entry: medium, high
- Age category: adults (≥ 65), adults (≥ 18 to < 65) and adolescents (≥ 12 to < 18)
- Gender: Male, Female
- Race: White, Black or African American, Asian, Other
- Exacerbations in the year before study: ≤ 2 exacerbations, > 2 exacerbations
- OCS at baseline: present, absent
- Baseline body mass index (BMI): < 18.5 kg/m², 18.5 - < 25.0 kg/m², 25.0 - < 30.0 kg/m², ≥ 30.0 kg/m²
- Geographical region: Asia Pacific, North America, South America, Central/Eastern Europe, Western Europe plus Australia, Rest of World
- Nasal polyps in the 2 years before randomisation: Yes, No

A similar negative binomial model will be fitted as for the primary analysis for each of the above variables in turn, with additional factors for the subgroup variable (where not already included) and the treatment by subgroup interaction. This model will be used to estimate the

treatment effect and its 95% CI within each of the subgroup categories, which will be tabulated and also summarised graphically using a forest plot. The overall treatment effect will be displayed on the forest plot.

For age, the above categorisation will replace the one used in the primary analysis model.

A p-value for the treatment by subgroup interaction will not be presented for each of these models due to the various difficulties in interpretation.

The standardised effect plot will be produced separately for:

- Subgroups defined using pre-specified categories (biomarkers of interest and other exploratory variables on the same plot)
- Subgroups defined using quartiles of the baseline data (biomarkers of interest only).

4.2.5 Key secondary endpoints

4.2.5.1 Main analysis

The main analysis of the key secondary endpoints (changes from baseline to Week 52 for each of pre-bronchodilator FEV₁, AQLQ(S)+12 total score, ACQ-6 score and weekly mean ASD score) will quantify the effect of the initially randomised treatment at Week 52, regardless of the treatments that subjects actually received, or whether the subjects received other controller therapy/rescue medications, including for subjects who discontinued study treatment prior to Week 52.

This analysis uses a treatment policy strategy and will therefore include all available data after treatment discontinuation until the end of the planned treatment period.

Subjects will be encouraged to continue to undergo applicable study related visits/procedures for the full 52-week period even after premature discontinuation of IP. Consequently, subjects lost to follow-up, subjects who die, subjects who withdraw their consent and subjects who choose Option 3 for their follow-up should be the only source of missing information for the key secondary analyses apart from subjects who choose Option 2 for their follow-up, who will have missing pre-BD FEV₁ following discontinuing of IP until their Week 52 visit.

Missing data will be modelled based on what was observed during the study using direct likelihood approaches, which is a valid approach under the assumption that data are missing at random (MAR).

Change from baseline for the key secondary endpoints in the tezepelumab group will be compared to that seen in the placebo group using a mixed model for repeated measures (MMRM) model. This model will be used to perform the statistical tests of the null hypotheses specified in [Section 4.1.1](#), and to estimate the treatment effect at Week 52 and its 95% confidence interval, for each endpoint.

The response variable in the model will be change from baseline at each scheduled post-randomisation visit up to and including Week 52, and irrespective of whether the subject remained on treatment and/or took other treatments. Treatment, visit, region, age (adolescents or adults) and treatment by visit interaction will be included as factors in this model. Baseline of the corresponding endpoint will also be included in the model as a continuous linear covariate. Baseline by visit interaction will not be included as a covariate in the MMRM model.

Unstructured covariance will be assumed to model the relationship between pairs of response variables taken at different visits on the same subject. To allow for the possibility that the MMRM model fails to converge with unstructured covariance, the following hierarchical approach is proposed to select a simpler covariance structure if the preceding covariance structure fails to converge: Unstructured → Heterogeneous Toeplitz → Heterogeneous First Order Autoregressive → Toeplitz → First Order Autoregressive → Compound Symmetry. Before concluding non-convergence at any step of this hierarchy, an attempt will first be made to resolve convergence problems by using different starting values of the underlying algorithm and/or adjusting singularity options. The Kenward-Roger approximation to estimating the degrees of freedom will be used for tests of fixed effects derived from the MMRM model.

For the ASD endpoint, each of the 52 weeks used for weekly mean calculation will replace visit in the above model specification.

Descriptive summaries of the key secondary endpoints will also be presented.

Adjusted means from the MMRM model above will be displayed graphically over time and used to evaluate time of onset of effect. Adjusted means will be calculated from the MMRM using the observed margins approach, in which the contribution of model factors to the estimate is weighted proportionally to the presence of these factors in the data.

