9.4.3.2 Analysis of key secondary efficacy endpoints

The main analysis of the key secondary endpoints (changes from baseline to Week 52 for each of pre-bronchodilator FEV1, AQLQ(S)+12 total score, ACQ-6 score and weekly mean ASD score) will quantify the effect of the initially randomized treatment at Week 52, regardless of the treatments that subjects actually received, or whether the subjects received other controller therapy/rescue medications, including for subjects who discontinued study treatment prior to Week 52. This analysis will therefore include all available data after treatment discontinuation. Missing data from study discontinuation will be modelled based on what was observed during the study using direct likelihood approaches, which is a valid approach under the assumption that data are missing at random (MAR).

Change from baseline for the key secondary endpoints in the tezepelumab group will be compared to that seen in the placebo group using a mixed model for repeated measures (MMRM) model. This model will be used to perform the statistical tests specified in Section 9.1,

and to estimate the treatment effect at Week 52 and its 95% confidence interval for each endpoint. The response variable in the model will be change from baseline at each scheduled post-randomization visit up to and including Week 52, and irrespective of whether the subject remained on treatment and/or took other treatments. Treatment, visit, region, age (adolescents or adults) and treatment by visit interaction will be included as factors in this model. Baseline of the corresponding endpoint will also be included in the model as a continuous linear covariate. Unstructured covariance will be assumed to model the relationship between pairs of response variables taken at different visits on the same subject. If the MMRM model fails to converge with unstructured covariance, the SAP will pre-specify the approach for selecting a simpler covariance structure. The Kenward-Roger approximation to estimating the degrees of freedom will be used for tests of fixed effects derived from the MMRM model.

Descriptive summaries of the key secondary endpoints will also be presented. Adjusted means from the MMRM model above will be displayed graphically over time and used to evaluate time of onset of effect.

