1.3 Number of subjects

Approximately 1060 subjects will be randomly assigned to study treatment using 1:1 allocation between the two treatments. Since the primary analysis of the primary endpoint will include all available data, including after treatment discontinuation, no need is envisaged to adjust the number of subjects planned to be randomised in order to obtain a number of evaluable subjects.

With 530 subjects per treatment group it is estimated that, using the multiple testing procedure described in [Section 4.1.2](#) with an overall Type 1 error control at $\alpha=0.05$ and a Type 1 error control for the primary endpoint at $\alpha=0.01$, the power for the primary and the key secondary endpoints will be at least 90%. The Type 1 error control at $\alpha=0.01$ for the primary endpoint is chosen to further ensure statistically persuasive evidence.

For the primary endpoint, assuming a placebo rate of 0.9 per year, a shape parameter of 2.4 (overdispersion), and a dropout rate of 10% (assumed uniform over the study), there will be at least 99% power to detect a rate reduction of 50% at a 2-sided significance level of 1%. The methodology used is as described in [Keene et al., 2007](#), and developed further by [Zhu and Lakkis, 2014](#). The minimum rate reduction that would yield statistical significance with the above assumptions is 27%.

For AAER in subjects with baseline eosinophils $< 300/\mu\text{L}$, assuming a placebo rate of 0.6 and assuming that half of subjects will be in this subgroup (i.e. 265 subjects per treatment group), there will be 94% power to detect a rate reduction of 50% at a 2-sided significance level of 5%, with the same shape parameter and dropout assumptions as above.

For each of the following four key secondary endpoints, change from baseline in pre-BD FEV₁, change from baseline in AQLQ(S)+12 total score, change from baseline in ACQ-6, and change from baseline in weekly mean Asthma Symptom Diary score, the nominal power is 95% or higher (using a nominal 2-sided significance level of 5%), assuming standard deviations of 400 mL and 1.3, 1.3, and 1.3 units respectively, and true differences of 100 mL and 0.3, 0.3, and 0.3 units respectively. The minimum detectable differences, under the above assumptions, are 50 mL for FEV₁, 0.16 for AQLQ(S)+12 total score, and -0.16 for each of Asthma Symptom Diary score and ACQ-6 score.

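### One baseline slope pooled over all visits may cost some Week 52 precision for pre-BD FEV1, AQLQ(S)+12 and ACQ-6; visit-specific slopes would protect it at almost no cost

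*SAP*

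**What the plan says.** SAP 4.2.5.1 defines one MMRM for the four key secondary endpoints. On baseline it says: "Baseline of the corresponding endpoint will also be included in the model as a continuous linear covariate". It then closes off the visit-specific version: "Baseline by visit interaction will not be included as a covariate in the MMRM model". The covariance is flexible: "Unstructured covariance will be assumed to model the relationship between pairs of response variables taken at different visits on the same subject", with a list of simpler structures if the fit does not converge.

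Protocol 9.4.3.2 gives the same terms: "Treatment, visit, region, age (adolescents or adults) and treatment by visit interaction will be included as factors in this model", plus baseline as a linear covariate. The SAP therefore follows the protocol. Neither document explains the exclusion, and no sensitivity analysis adds the term.

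For the ASD score, "each of the 52 weeks used for weekly mean calculation will replace visit in the above model specification".

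Only the Week 52 contrast is tested (SAP 4.1.1). SAP 1.3 states nominal power of at least 95% for each key secondary endpoint with 530 subjects per group.

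**The concern.** Baseline is in the model to remove between-subject variance from the Week 52 comparison. It does this best when the slope is the one that holds at Week 52. With a single slope, generalised least squares pools over visits and gives most weight to those where baseline predicts well. Those are likely to be the early ones, and the schedule is front-loaded: five of the eight post-baseline FEV1 visits fall by Week 16. If the regression of change on baseline steepens during the year, the pooled slope is too shallow for Week 52 and residual variance there is larger than it need be.

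The precision at stake is that of H03, H04a and H04b. AQLQ(S)+12 and ACQ-6 are also judged at 3.75% and 2.5% under the truncated Hochberg step (SAP 4.1.2), where there is less power to spare.

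**Working it through.** **Plan's own figures (SAP 1.3).** n = 530 per group, two-sided 5%.
- SE for the 1.3-unit endpoints: 1.3 × √(2/530) = 0.0799. Effect/SE = 0.3/0.0799 = 3.757. Power = Φ(3.757 − 1.960) = 96.4%.
- FEV1: 400 × √(2/530) = 24.57 mL. 100/24.57 = 4.070. Power = Φ(2.110) = 98.3%.
- Smallest significant differences: 1.96 × 24.57 = 48.2 mL (stated 50) and 1.96 × 0.0799 = 0.157 (stated 0.16).

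The stated power reproduces, and it does not depend on the baseline term.

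**Visit schedules (protocol Table 2, post-baseline).** FEV1: Weeks 2, 4, 8, 12, 16, 24, 36, 52 (8 visits). AQLQ(S)+12: Weeks 4, 12, 24, 36, 52 (5). ACQ-6: Weeks 2 and 4, then 4-weekly to 52 (14).

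**Formula.** Let β be the vector of visit-specific slopes of change on baseline and S the residual covariance between visits. In large samples the pooled slope is b = (1′S⁻¹β)/(1′S⁻¹1). Relative to visit-specific slopes, Week 52 variance is multiplied by 1 + (β₅₂ − b)² × Var(baseline)/σ²₅₂.

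**Assumptions, none from the documents.** The SD is equal at all visits, so β_t = r_t − 1 and σ²_t/Var(baseline) = 1 − r_t², where r_t is the correlation with baseline. r_t changes linearly in √week from the first visit to Week 52. The residual correlation is 0.6 between all visits.

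| r, first visit to Week 52 | Endpoint | β₅₂ | b | Variance inflation |
|---|---|---|---|---|
| 0.7 to 0.7 | all three | −0.300 | −0.300 | 0% |
| 0.8 to 0.7 | FEV1 | −0.300 | −0.221 | 0.079²/0.51 = 1.2% |
| | AQLQ(S)+12 | −0.300 | −0.232 | 0.068²/0.51 = 0.9% |
| | ACQ-6 | −0.300 | −0.222 | 0.078²/0.51 = 1.2% |
| 0.85 to 0.65 | FEV1 | −0.350 | −0.150 | 0.200²/0.5775 = 6.9% |
| | AQLQ(S)+12 | −0.350 | −0.174 | 0.176²/0.5775 = 5.4% |
| | ACQ-6 | −0.350 | −0.133 | 0.217²/0.5775 = 8.2% |

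The ACQ-6 value of b lies just outside the range of the visit slopes because generalised least squares weights can be negative. If the residual correlation instead falls with the gap between visits, from about 0.8 to 0.4, the 0.85-to-0.65 case gives about 4% for each endpoint.

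**Effect on power, if 1.3 is the SD attained with visit-specific slopes.** With 8% inflation, 3.757/√1.08 = 3.615 and power = Φ(3.615 − 1.960) = 95.1%, down from 96.4%. At 3.75% it goes from 95.3% to 93.8%, and at 2.5% from 93.5% to 91.5%. At 5%, power drops below 95% only if variance rises by more than 8.6% (1.3-unit endpoints) or 27% (FEV1).

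**If 1.3 is instead the SD of raw change.** Adjustment at r = 0.65 multiplies variance by (1 + 0.65)/2 = 0.825. AQLQ(S)+12 power is then about 98.5% with visit-specific slopes and 98.1% with the common slope. Both exceed the stated figure.

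**Simulation check.** AQLQ(S)+12 schedule, 530 per group, about 10% dropout missing at random, 500 trials per scenario, both models fitted by likelihood. The SE ratio (common over visit-specific) was 1.000 with constant correlation and 1.028 for 0.85 to 0.65 (1.028² = 1.057, so 5.7% in variance). Mean Week 52 estimates were 0.228 to 0.232 against a true 0.23 under both models. In the 0.85-to-0.65 case the common-slope model's SE matched its empirical SD (0.049 and 0.049).

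**The case against.** The strongest objection is that slope drift is assumed. Neither document gives a baseline-to-visit correlation, and with constant correlation nothing is lost. That stands, and it is why the size is a range that includes zero. A much steeper fall would cost more: 0.9 to 0.5 gives 18 to 36% on these schedules. Nothing in the documents supports planning on that.

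For ACQ-6 the equal-SD assumption may also flatter the effect. Inclusion criteria 11 and 16 require a score of at least 1.5 at screening and at randomization, which trims baseline variance. Inflation is proportional to that variance, so halving it with slopes and residuals unchanged would turn 8.2% into 4.1%. The amount of trimming is unknown.

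The choice is also pre-specified and agrees with the protocol. That stands too: this is an efficiency point, not an inconsistency.

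A reader might infer more than the documents support:
- *That Week 52 is wrongly adjusted and the test unsound.* Allocation is randomised, treatment by visit is in the model and the covariance is unstructured. The simulation showed no material bias.
- *That predictions of missing Week 52 values are distorted.* The simulation with dropout shows no material harm. The imputations in SAP 4.2.5.2 run one time point at a time with baseline included, so their slopes are not forced to be equal.
- *That the restriction has no benefit anywhere.* For ASD it does. The 52-level unstructured covariance has 52 × 53/2 = 1,378 parameters, and keeping 51 further slopes out is defensible.

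**Conclusion.** For pre-BD FEV1, AQLQ(S)+12 and ACQ-6, the common slope cannot improve Week 52 precision in large samples and may reduce it. The loss in variance is 0% without drift, about 1% for a fall in correlation from 0.8 to 0.7, and about 4 to 8% for 0.85 to 0.65. At the upper end of that range the power cost at two-sided 5% is about 1.3 percentage points for the two questionnaire endpoints, and power stays above the stated 95%. These sizes rest on equal SDs, the assumed correlation paths, and reading 1.3 as the SD attained with visit-specific slopes. The documents settle none of these.

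This is a small, optional improvement. It does not put the validity of the analysis or the stated power in doubt, and it does not extend to ASD.

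**What to change.** In SAP 4.2.5.1, replace the exclusion with: *For pre-BD FEV1, AQLQ(S)+12 total score and ACQ-6 score, the MMRM will include the baseline by visit interaction; for the ASD score it will not.* Record this in SAP Section 6 as a change from protocol 9.4.3.2, before primary database lock. Analyses that reuse this model (SAP 4.2.5.2, 4.2.5.3, 4.2.5.5 and Appendix 8.4) should follow it. The analysis of the imputed datasets would then also match the visit-by-visit regressions used to create them.

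The cost is two short text changes and 7 (FEV1), 4 (AQLQ(S)+12) and 13 (ACQ-6) extra slopes. With about 1,060 subjects that is negligible: the simulated SE ratio was 1.000 when the slopes were truly equal. If the sponsor prefers to keep the main model, it should state the reason and add the interaction as a sensitivity analysis for these three endpoints.
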